9.8.1 Qualitative sub-study follow up

Women

A purposive sample of approximately 30-40 participating women from both arms of the study will be invited to take part in longitudinal interviewing (at up to three time points, to include point of entry if practical and after the 22-39 week follow-up) to understand the day-to-day operation of the trial and impacts on daily life. Upon invitation, they will be asked if they would like to take part in the optional photovoice activity designed to support the interview(s). Should they decline to take part in the photovoice activity, they will still eligible to take part in an interview(s). In addition, we will include a sample of up to eight women who decide not to take part or withdraw, but who and are willing to be interviewed. We will recruit women from across the study sites and aim for a diverse sample, to help understand the real-life implementation issues with self-management postnatally. Purposive sampling will include women from central and peripheral hospital settings, a range of ages, socio-economic and ethnic background, parity, previous history of raised BP in pregnancy or pre-eclampsia. This will be assessed as participants start being contacted for the qualitative sub-study interviews.

Following consent to the qualitative study, semi structured interviews will be conducted with participants in both arms to assess their experience of either usual care or self-management of blood pressure in the postnatal period, and to identify and explore factors related to the successful (or unsuccessful) implementation of the intervention. Participants who consent to take part in the photovoice activity will have a short phone or video call with the qualitative sub-study researcher prior to the interview to discuss the activity in greater detail, including discussion around how to obtain permission for and safely take photographs. Participants will then take photographs on their smartphone that reflect their experiences of managing their blood pressure in the postnatal period. They will share these photographs with the

qualitative sub-study researcher prior to, or during, the interview by uploading them to a secure online folder in OneDrive. A link to this folder will be shared with the participant in an email. Photographs will then be looked at together by the researcher and the participant to aid reflection on the participant's experience of either usual care or self-management. Taking part in the photovoice activity will not require participants to undertake any additional interviews.

This embedded study will provide data regarding the views of participants as to the acceptability of self-monitoring and self-management in the routine management of gestational hypertension and pre-eclampsia after birth, once they have been discharged from hospital. The control group will be interviewed to allow comparison of participant experience in the two arms. Individuals who decline to participate in the main trial and those who subsequently withdraw from it, will still be invited to contribute an interview, as this will provide valuable insights into the acceptability of the intervention.

A subset of these interviews may be conducted by community-based researchers with translation where needed. The interviews will be at various time points during trial participation, allowing for flexibility around women's preferences. Interviews will be offered remotely (via telephone or videoconferencing) or face-to-face, with timing sensitive to the competing demands for a woman in the postnatal period, and last approximately 30-60 minutes. Interviews will be audio-recorded for transcription and analysis. We will offer text relay to support women who may have hearing conditions and to ensure non-English speakers are included, we will offer the use of an established telephone translation service such as 'Language Line'. Participants will be offered a voucher to thank them for their time.

Healthcare professionals

Semi-structured interviews will be conducted with 25-30 participating healthcare professionals (including obstetricians, midwives and GPs) involved in the study. Sampling for these interviews will be from across participating sites, and focus on ensuring staff perspectives provide insights into their experiences of using the intervention with diverse groups of women. Interviews will be offered remotely (via telephone or video-conferencing) or face-to-face and last approximately 30-60 minutes. Interviews will be audio-recorded for transcription and analysis. These will aim to understand how self-management is operationalised in practice.

9.9. Sample Handling

At the 6 week (+/-3) follow-up, participants will be asked to provide a minimum of a 10ml urine sample in a standard plastic container. Each sample will be transferred from the clinic site/participant's home to the laboratory at University Hospitals of Leicester at room temperature, via a Royal Mail next day delivery service. Samples remain stable for 72 h after collection.

All samples received by the laboratory will be analysed on a rolling basis. LC-MS/MS will be performed to detect all antihypertensive drug classes. The test is a standard laboratory test that is accredited by United Kingdom Accreditation Service (UKAS). Samples will be stored for up to 1 year after the end of the study declaration for quality checking/verification of the research, following which they will be stored for 5 years after the end of the study at a HTA licensed facility. The storage for 5 years after the end of the study is in case of future research, which participants will be asked to consent to.

9.10. Early Discontinuation/Withdrawal of Participants

During the course of the study a participant may choose to discontinue early from the study intervention at any time. This may happen for several reasons, including but not limited to:

- The occurrence of what the participant perceives as an intolerable AE related to the intervention.
- Inability to comply with study procedures
- Participant decision

Participants may choose to stop intervention and/or study assessments including urinary sample provision, but may remain on study follow-up.

Participants may also withdraw their consent to withdraw from the study completely. In the case of withdrawal from both treatment and active follow up, a participant's data and samples obtained up until the point of withdrawal will be retained for use in the study analysis. No further data or samples would be collected after withdrawal.

In addition, the Investigator may discontinue a participant from the study treatment at any time if the Investigator considers it necessary for any reason including, but not limited to:

- Ineligibility (either arising during the study or retrospectively having been overlooked at screening)
- Significant protocol deviation
- Clinical decision
- Loss of capacity to consent to involvement in research, for example due to developing puerperal psychosis
- Loss to follow up

Non adherence in either group would be defined as missing a trial visit, and not being contactable to reschedule the visit. Non adherence in the intervention arm is defined as failing to report 3 consecutive blood pressure readings in the first 14 days after birth, or 5 consecutive blood pressure readings from this point onwards. The definition of "significant non adherence necessitating discontinuation from the study" will be an individualised judgement made by the research team in conjunction with a participant's direct care team. This judgement will be made on the basis of concerns regarding participant safety, and therefore will be influenced by the nature, frequency and clinical impact of a particular participant's non-adherence.

If a participant from the intervention arm discontinues from the study, they will continue usual postnatal care including blood pressure monitoring with their community midwife and GP.

The level of discontinuation or withdrawal and reason will be recorded in the CRF. If the participant discontinues or withdraws due to an adverse event, the Investigator will attempt to contact the participant's clinical care team for information until the adverse event has resolved or stabilised.

9.10.1 Qualitative sub-study

Women are eligible for this sub-study even if they withdraw from the trial. Healthcare professionals who choose to take part in the qualitative sub study will be free to withdraw if they decide they no longer want to take part.

Participants will be free to terminate a scheduled interview, the photovoice activity, or the interview itself at any point. Once they have participated in the interview they will have two weeks to withdraw from the study should they wish to; this will be made clear at the point of recruitment and at the end of the interview. If the participant withdraws from the sub-study within two weeks, their data (personal data, interview data including transcripts and recordings, and photographs if shared) will be securely destroyed. After two weeks, participant de-identified data will be incorporated into the body of the analyses but illustrative quotes from the interviews and any photograph taken by the participant will not be used in any outputs.

9.11. Health equity

Trial populations tend to include a larger proportion of affluent individuals than society as a whole. To address this, the SNAP2 trial aims to support health equity, in an effort to acknowledge that a lack of inclusionary practice can potentially increase health disparities and that outcomes for women are not equal. There remain stark gaps in maternity outcomes between women from Black, Asian, mixed and white ethnic groups and research aimed at improving care for women must seek to understand and address these disparities. Recognising that it is challenging to recruit participants from socially disadvantaged or ethnic minority groups unless proactive steps are taken to include them, we will engage with these communities throughout the trial to ensure that our materials are relevant and accessible to all women (Khunti K, 2020), (Prinjha S, 2020), (Darko, 2021) . We have engaged with third-sector organisations and community groups during the intervention and protocol development to ensure inclusion across the programme.

Trial recruitment: working with our co-applicants and PPI groups, inclusive recruitment routes have been devised aiming to ensure a diverse sample is included in the trial (Dawson S, 2022). This includes targeted selection of NHS trusts through which to recruit and engagement with community organisations. Electronic data collection will allow real-time assessment of the success of this approach, allowing iterative changes in process should initial results fall short of expectation. This builds on approaches used successfully in our previous pregnancy and postnatal trials which have recruited women representative (from an ethnicity perspective) of the wider pregnancy population. An information video will be created with a voiceover to explain the study in simple terms to aid recruitment.

Process evaluation (qualitative sub study): Understanding how the intervention has worked in practice for women and healthcare professionals from all parts of the population is important, particularly if the results from subgroups based on ethnicity or deprivation suggest any differences. Our qualitative work will include purposively sampling will ensure the experiences and perspectives of women from socioeconomically deprived and/or ethnically diverse groups will be included.

Community based (peer) researchers: in order to ensure that the issues most important to women from diverse backgrounds are addressed in the process evaluation, community based (peer) researchers will be recruited through our PPI contributor networks and contracted on a consultancy basis. These community researchers will support research with minority ethnic groups that are often harder to reach in research. They will provide support to participate in up to 15 of the interviews described (plus translation costs). This will help to maintain the focus on health equity issues in the trial analysis.

Intervention and language: During intervention development we considered translation of the intervention. Latest census figures published by the government indicate that 3.1% of the population could not speak English at all ((ONS), 2021). These rates are highest among older groups (GOV.UK, 2020). Women aged 15-44 the range of people who couldn't speak English ranged from 0.1-2.8%, and those in the younger 10-24 age group the range was 0.1-0.7%. The usage of internet translation applications (e.g. Google Translate) or Language Line is highly prevalent. We have therefore concluded that it is reasonable to provide the intervention and study materials in English, using Inclusive Communication Guidance as a guide to plain English (GOV.UK, 2021).

9.12. Internal Pilot Phase and Stop Go Criteria

We will incorporate an internal pilot phase into the study. We will aim to recruit the first 100 participants within 6 months to prove that the trial is feasible. Following the 6 month period, the following Stop/Go criteria will be applied before transition to the main trial:

Table 1: Recruitment criteria in the first 6 months from 1st randomisation.

Number of participants recruited	Proposed Action		
> 100 Participants	No change to trial		
▶ 80-99	Careful review of trial		
	procedures and inclusion		
	criteria.		
▶ 60-79	Careful review of trial		
	procedures and inclusion		
	criteria as above but substantial		
	changes may		
	be needed		
> < 60	Discussion with sites, sponsor		
	and funders regarding feasibility		
	of continuing trial due to		
	possible futility of recruitment.		
 Recruitment per site: ste 	eady state of at least 1.5 women		
per month per site. Sites	per month per site. Sites recruiting <1 women per month		
for 3 months in a row w	for 3 months in a row will be considered for		
decommissioning.			
 Proportion of those recr 	Proportion of those recruited from the relative		
deprivation/ethnic minority groups will be reviewed in the			
first 100 women. Although this will not be a formal stop/go			
criteria, adjustments will be made if the initial recruitment			
population appears not to be generalisable.			

9.13. End of Study Definition

The end of study is the date of the last data collection and cleaning prior to data lock or end of qualitative data collection, whichever is later. Samples will be stored for up to 1 year after the end of the study declaration for quality checking/verification of the research but the end of study date will be declared once all data collection and cleaning has been completed.

10. SAFETY REPORTING

10.1. Adverse Event Definitions

Adverse	Event (AE)		Any untoward medical occurrence in a participant, which does not necessarily have a causal relationship with the trial intervention.
Serious (SAE)	Adverse	Event	 A serious adverse event is any untoward medical occurrence that: results in death is life-threatening requires inpatient hospitalisation or prolongation of existing hospitalisation results in persistent or significant disability/incapacity consists of a congenital anomaly or birth defect*. Other 'important medical events' may also be considered a serious adverse event when, based upon appropriate medical judgement, the event may jeopardise the participant and may require medical or surgical intervention to prevent one of the outcomes listed above. NOTE: The term "life-threatening" in the definition of "serious" refers to an event in which the participant was at risk of death at the time of the event; it does not refer to an event which hypothetically might have caused death if it were more severe.

10.2. Reporting Procedures for Adverse Events

Safety reporting will be from baseline to the 22-39 week follow up visit.

We do not anticipate that the study intervention (reporting of self-monitoring of BP via an app) should result in any adverse events (AEs), but include this section in case such events are reported at each study visit, so that they can be considered for causal links to the study.

Generally speaking, only unexpected adverse events* that are clinically judged (by the supervising site PI) as being caused by the trial intervention will be reported to the PC-CTU, who will inform the REC that gave favourable opinion in case of unexpected related serious adverse events. The supervising site PI should assess each adverse event's expectedness using the information below in Section10.3, and only report those which are judged to be unexpected. We will not ask for side effects as stated in the BNF to be reported as AEs, as these will be deemed expected adverse events.

*The only exception to this rule is that stroke, intracranial haemorrhage and seizure will always be reportable to the PC-CTU regardless of expectedness. Please also see Section 10.4.

Expected Adverse Events

The adverse events described below are expected to occur in this participant population and will not be classified or reported as SAEs, unless felt to be directly related to the study intervention. The CI will also review the AEs for expectedness – in cases of uncertainty, this will be ratified by the steering group.

- Admission for monitoring for hypertension
- Admission for psychiatric or social reasons
- Admission for postpartum complications (for example wound infection following surgery, mastitis, urinary tract infection)
- Known complications of postnatal hypertension that are collected for every woman as part of outcome collection
- Known side effects of prescribed medications as listed in the BNF
- Admission of the woman due to complications with the baby (including but not limited to neonatal jaundice, need for respiratory support, seizures, congenital anomaly)
- Pre-planned admission (e.g planned surgery)
- Side effects as stated in the BNF

10.3. Reporting procedures for Serious Adverse Events

Please see Section 10.3 regarding SAEs which will be reported as outcomes, so do not need to be reported as SAEs.

All serious adverse event (SAE) information must be reported on the PC-CTU SAE report form by the site and emailed to the trial inbox, which is monitored during office hours. SAEs will be reported to the PC-CTU as soon as possible, preferably within 24 hours of the site becoming aware of the event. The PC-CTU will perform an initial check of the report, request any additional information from the reporting clinician and ensure that the CI or safety delegator reviews and evaluates the report to confirm expectedness and relatedness. All SAE reports will also be reviewed routinely by the Data Monitoring and Ethics Committee, and all SAEs will be followed up until resolution or the end of the study period.

A SAE occurring to a participant should be reported to the REC that gave a favourable opinion of the study, where in the opinion of the Chief Investigator the event was 'related' (resulted from administration of any of the research procedures) and 'unexpected' in relation to those procedures. Reports of related and unexpected SAEs should be submitted within 15 working days of the Chief Investigator becoming aware of the event.

10.4. Expected Serious Adverse Events

The following SAEs (which must also fulfil at least one of the criteria listed in section 10.1) may be expected to occur in this population, as they relate to the disorder being investigated (pregnancy and associated hypertensive diseases). These will be collected as outcomes and do not need to be reported as SAEs.

Potentially related to BP management	Unrelated to BP management
BP ≥ 160/110 mmHg	Vaginal bleeding
BP < 90/50 mmHg whilst on treatment	Endometritis
	Sepsis
Faint	Pyelonephritis
Fall	Mastitis
Headache	Surgical site infection
Vomiting	Paralytic ileus
Upper abdominal pain	Visceral injury (ureter, bladder, bowel)
	Pelvic collection
	Haematoma

Regardless of whether they might be expected in this population, the following serious adverse events will be reported as SAEs:

- Stroke
- Intracranial haemorrhage
- Seizure

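### Section 10.4 exempts its listed expected SAEs from SAE reporting at any severity, so a fatal or life-threatening listed event judged unrelated has no guaranteed prompt route to the trial unit

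*Protocol*

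**What the plan says.** Section 10.1 gives the usual seriousness criteria; "results in death" is the first, and threat to life is the second.

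Section 10.4 sets out two columns of events, one possibly connected with blood pressure management and one not. The introduction reads "The following SAEs (which must also fulfil at least one of the criteria listed in section 10.1) may be expected to occur in this population", and the instruction is "These will be collected as outcomes and do not need to be reported as SAEs". A short list follows under the words "Regardless of whether they might be expected in this population, the following serious adverse events will be reported as SAEs"; it names stroke, intracranial haemorrhage and seizure and nothing else.

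Section 10.2 says the same of the trial unit: "The only exception to this rule is that stroke, intracranial haemorrhage and seizure will always be reportable to the PC-CTU regardless of expectedness". It has its own list of expected events, which "will not be classified or reported as SAEs, unless felt to be directly related to the study intervention". That list partly overlaps the one in 10.4, for example through "Known complications of postnatal hypertension that are collected for every woman as part of outcome collection", admissions for postpartum complications, and known drug side effects. It adds a second look: "The CI will also review the AEs for expectedness", with uncertain cases going to the steering group. No time limit is attached to that review.

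Section 10.3 sets the prompt route: a form to the trial unit with a 24-hour target, a check of expectedness and relatedness by the chief investigator or a delegate, and routine review of SAE reports by the monitoring committee. Its opening line leaves out SAEs that are handled as outcomes.

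**The concern.** An exemption for expected events usually aims to spare sites the paperwork for common, foreseeable admissions. Here it is tied to the event name and to meeting any seriousness criterion, so it also covers the worst cases under that name. A mastitis admission and a death from sepsis are treated alike.

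At stake is the independence of the relatedness judgement. The 10.3 procedure has someone other than the site confirm whether an event was related. For a listed event, the site's own view that it was unrelated is what keeps the event out of that procedure. The trial is unblinded at site level (section 9.5), and the intervention changes how antihypertensive doses are adjusted. Section 5.2 itself names iatrogenic hypotension as a risk in this population, and low blood pressure on treatment, faints and falls are among the exempt events.

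**Working it through.** No sample size or error-rate figure is involved, so the check is to follow cases through sections 10.1 to 10.4.

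**Case A: fatal sepsis, judged unrelated by the site.**
1. 10.1: serious, because fatal.
2. 10.4: sepsis is listed, and any 10.1 criterion qualifies, so it is exempt.
3. Always-report lists in 10.2 and 10.4: it is not stroke, intracranial haemorrhage or seizure.
4. 10.2 relatedness exception: not met.
5. 10.2 general rule: only unexpected events judged to be caused by the intervention go to the trial unit. Not met.
6. 10.3: SAEs handled as outcomes are left out. The cross-reference there points to 10.3 itself, but evidently means 10.4.

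Result: no SAE report is required.

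**Case B: life-threatening BP <90/50 mmHg on treatment, judged unrelated.** The steps and the result are the same.

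**Case C: a listed event judged directly related.** Section 10.2 brings it back into SAE reporting where it falls within the 10.2 list. Section 10.4 does not repeat the exception, so an event named only in 10.4 is left unclear.

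**Case D: fatal stroke.** Always reported.

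The gap therefore consists of cases A and B.

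**What else would capture such an event?**

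| Route | Source | Limit |
|---|---|---|
| Adverse event questions at visits | 9.8 | Put to the participant, so survived events only |
| Records review of all-cause admissions, pregnancy hypertension admissions and cardiovascular events | Section 6 | Done at the end of the trial period |
| Review of expectedness by the chief investigator and steering group | 10.2 | No timing stated |
| General safety remit of the monitoring committee | 13.3 | Details are in a charter that is not shown |

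Death is not a named outcome in section 6.

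For survived life-threatening events, the visit windows in 9.8 give the spacing of the questions:
- first visit: 6 − 3 = 3 weeks to 6 + 3 = 9 weeks after randomisation;
- second visit: 12 − 4 = 8 weeks to 12 + 4 = 16 weeks;
- second to third visit (22–39 weeks): at least 22 − 16 = 6 weeks and at most 39 − 8 = 31 weeks.

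These intervals say nothing about delay for deaths.

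**Extra reports if the rule is changed.** The protocol gives no rate. For scale only, with about 690 women, each 0.1% affected is 0.001 × 690 = 0.7 report. An assumed range of 0 to 1% gives 0 to 0.01 × 690 = 6.9 reports.

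**The case against.** The strongest reply is proportionality. The intervention is home monitoring and an app added to usual care, section 5.4 anticipates low risk, and collecting condition-related events as outcomes is a deliberate choice. That stands as a reason to keep the exemption for ordinary listed events. It is not a reason to include deaths.

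The wording is also permissive. Saying that a report is not needed does not forbid one, and a site might treat a fatal fall as unexpected. But 10.4 admits events under any 10.1 criterion, so a site that withholds the report is following the rule exactly.

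Some stronger inferences are tempting and should not be drawn:
- *That these events are lost.* The documents do not support this. Admissions and cardiovascular events are reviewed from records, and survived events can surface at visits.
- *That nobody but the site ever looks.* Section 10.2 provides for the chief investigator and steering group to review expectedness, and the unseen charter may give the monitoring committee further data. The protocol shows neither prompt nor late review by these routes; it guarantees none that is prompt.
- *That related events are equally exempt.* Section 10.2 covers much of that ground, and 10.4 merely fails to repeat it.

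It is also fair to say that ethics committee reporting would not change, since 10.3 reserves it for events both related and unexpected. In the intervention arm, abnormal readings already prompt clinicians (9.6.1), so individual blood pressure safety there does not rest on SAE forms.

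**Conclusion.** The point holds as a gap in prompt reporting and oversight. Under the rule as written, a fatal or life-threatening listed event judged unrelated requires no 24-hour report, no check of the site's relatedness judgement under 10.3, and no SAE report for routine committee review.

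The number of women affected cannot be derived from the protocol and may be zero; the 0 to 1% range is an assumption used only for scale. No endpoint, analysis or power figure depends on it. The conclusion rests on reading 10.4 literally and on the protocol alone; a charter or site instruction requiring immediate notification of deaths would narrow it. The change is worth making because it closes a safety gap at very small cost, not because the documents show that harm has been missed.

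**What to change.** 1. Add to the always-report lists in both 10.2 and 10.4: *any event that results in death or is life-threatening, regardless of expectedness or cause*.
2. Add to 10.4 a sentence repeating the 10.2 exception: *any listed event felt to be directly related to the study intervention is also reported as an SAE*.
3. Keep the exemption for all other listed events.

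This takes one line in each of two lists and one sentence, at the next amendment, with a note to sites so that women still within the safety reporting period are covered. The existing form, trial unit check and committee review are used. The downside is a few extra SAE reports, of unknown number. Item 2 may add some of its own, because several listed events are ones that the protocol itself links to blood pressure management, though 10.2 already makes many of these reportable when judged related.
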